7.5 Data Collection and Transfer Methods

Data collected will need to be directly entered by the research team at the local hospital onto the Sponsor's central database (eCRFs). Data collected by the blinded independent clinical development specialist will be directly entered onto the Sponsor's central database (eCRFs). Blinded independent clinical specialists will be given restricted access to the central database in order to prevent unblinding.

Imaging scans (MRI, CT and ultrasounds) will be transferred by sites to University College London (UCL) where they will be uploaded to the Data Safe Haven portal. Please refer to the trial specific SOP for details.

Training on data collection, secure data transfer and storage for site staff listed on the delegation of responsibilities log will be provided at the site initiation meeting(s).

7.6 Data Management

Data will be collected at the time-points indicated in the Participant Timeline (Section 5.2). Data will be entered under each participant's assigned trial specific PIN onto the central database. The database software provides a number of features to help maintain data quality, including maintaining an audit trail, allowing custom validations on data, allowing users to raise data query requests, and search facilities to identify validation failure and missing data.

Data collection, data entry, queries raised by a member of the ENLIVEN-UK trial team and database lock(s) will be conducted in line with the CCTU SOPs and trial-specific Data Management Plan.

The database will be password protected and only accessible to members of the ENLIVEN-UK trial team at CCTU, delegated site staff and external regulators if requested. Database users will only be granted permissions to use the database functionality appropriate to their role in the clinical trial.

Identification logs, screening logs and enrolment logs will be completed and held at the trial site.

7.6.2 Handling of imaging data

Ultrasound and MRI scans will be performed at the timepoints indicated in Section 5.3.1. Investigators are required to submit images of Ultrasound and standard of care MRI and CT scans for review and storage for all infants. Once ultrasound scans are performed the images will be transferred to UCL for secondary outcome analysis. Images will be pseudonymised by sites, with participant's names and hospital/NHS numbers removed.

A quality control (QC) check will be performed at UCL to ensure that all identifiable data has been redacted before the scan images are transferred using a secure method to the dedicated project area in UCL Data Safe Haven Pseudonymised images will be stored in a dedicated project area on the UCL Data Safe Haven.

All data will be handled in accordance with the Data Protection Act 2018, the EU General Data Protection Regulation (GDPR) 2016 (and subsequent updates and amendments).

7.7 Data Storage

Trial data will be stored in a database created specifically for the ENLIVEN-UK trial. The database is hosted by OpenClinica. The data are stored on secure, GDPR-compliant, cloud-based servers held within UK and EU: https://www.openclinica.com/privacy-policy/

The randomisation service is hosted by Sealed Envelope LTD. The data are stored on a secure, GDPR-compliant, cloud-based servers held within the EU: https://www.sealedenvelope.com/security/

The identification, screening and enrolment logs, linking personally identifiable information to the participant's trial specific PIN, will be held locally by the trial site. This will either be held in written form in a locked filing cabinet or electronically in password protected form on hospital computers. After completion of the trial the identification, screening and enrolment logs will be stored securely by the sites for 15 years after trial closure unless otherwise advised by CCTU.

7.8 Data Archiving

Once all primary and secondary analysis has been completed the trial data will be archived. Once the trial data has been archived the trial database will be decommissioned and will no longer be available. Any subsequent/further analysis will be performed using the archived data.

7.9 Quality Issues

Quality Issues are issues that can have an impact on patient safety, rights, and well-being; data integrity and/or scientific rigor; and compliance with regulatory requirements; these can be classified as protocol deviations, potential serious breaches, near misses etc.

A protocol deviation is any departure from procedures documented in this protocol, this includes deviations that cannot be predicted. If a protocol deviation is identified, the Trials team should be contacted and CCTU's protocol deviation reporting process will be followed.

A 'serious breach' is a deviation from procedures documented in this protocol, GCP or other clinical trial regulations that is likely to affect to a significant degree:

- 1. The safety or physical or mental integrity of the participants in the trial, or
- 2. The scientific value of the trial.

If a serious breach is suspected the Sponsor must be contacted within 1 working day. In collaboration with the CI, the serious breach will be reviewed by the Sponsor and, if

appropriate, the Sponsor will report it to the REC committee within 7 days of classification of a serious breach.

8 Statistical Considerations

8.1 Sample Size

The sample size required for the ENLIVEN-UK trial utilised individual patient data from the DRIFT trial, which showed that the distribution of cognitive quotient (CQ) in the 'standard treatment' arm at 2 years' corrected age was approximately uniform in the 0—100 interval with a median of approximately 50 (Figure 2a) (19). The distribution in the DRIFT arm was more skewed, with a median of approximately 70 (Figure 2a) (19). This was evident at 10 years, with a median difference of 25.6 (46.7 in the control arm vs 72.3 in the DRIFT arm) (13). We hypothesise that, mechanistically, NEL would achieve the same effect as DRIFT. We therefore estimate a median difference of 20 points between our treatment arms. A difference of 20 points is considered clinically significant, representing approximately a 5-month difference in developmental age at 2 years and a 2-year difference at 10 years. That this was also considered a significant and valuable difference to parents, as confirmed by a focus group led by our parent co-applicant [name].

To reflect results shown in DRIFT, the distribution of CQ in the control arm was modelled using a Beta(1,1) distribution, equivalent to the uniform distribution. The distribution in the experimental arm was modelled to be a Beta(10, 4.25). Both distributions were multiplied by 100 to reflect the 0—100 CQ scale (Figure 2b). Using simulations performed in R with 1000 replications, we established that 45 patients in each arm, totalling 90 patients, would provide 90% power to detect the hypothesised treatment effect, based on a Wilcoxon-test with two-sided alpha of 5%. To account for a 10% loss to follow-up and other methodological challenges during the study, we aim to recruit 100 patients in this study, 50 in each arm.

[figure not shown]

Figure 2: (a) Developmental quotient (old name for cognitive quotient on Bayley II) distributions in control (TD) and intervention (DRIFT) arms of the DRIFT trial. (b) Estimated distributions of cognitive quotient scores at 2 years in the control (TD) and intervention (NEL + TD) arms of the ENLIVEN-UK Study.

8.2 Assignment of Intervention

8.2.1 Randomisation Procedures

Following the Screening visit, the PI or delegate will enter the initials, gestational age at birth, sex, grade of IVH, site, re-confirm participant eligibility on the SealedEnvelope.com secure online system and allocate the appropriate trial specific PIN to the patient. Delegated staff at participating sites will be provided with a secure login to the SealedEnvelope.com website, according to their role in the trial. The randomisation result will be shown directly online as an arm allocation to the user in addition to an email, with an unblinded email confirmation of a successful randomisation sent to the CCTU trial team. Randomisation will be considered completed after intervention allocation has been assigned by the randomisation system.

8.2.2 Randomisation Methodology and Sequence Generation

A computer-generated randomisation sequence, using the SealedEnvelope.com system, will be used to assign the participants to one of the two treatment arms using a 1:1 ratio. The adaptive minimisation approach will be the treatment allocation methodology used to allocate treatment arms; while not allocating at random will be referred to as a 'randomisation method' here in ENLIVEN-UK. As per ICH E9 guidelines this will incorporate a random element into

each treatment allocation to avoid this approach being deterministic. This procedure will use a 'biased coin' approach where it will favour balance of arms with a high (80%) chance. The factors minimised on will not be provided here to reduce the chance of bias, but will be listed in the standalone Statistical Analysis Plan (SAP).

8.2.3 Allocation concealment mechanism and Blinding

This is a trial in which the primary outcome assessor, the Trial Statistician and the Clinical Project Manager will be blinded to the treatment allocation. The treating neurosurgeon and associated team cannot be blinded to treatment allocation due to nature of the study. Parents/legal guardians will be informed of the allocation after the procedure is completed. Parents will be informed by study team prior to the assessment that the assessor will be blinded to the treatment allocation, and they should therefore not divulge this information to the assessor inadvertently, which will be reinforced by the assessor before evaluation commences. All users of the Sealed Envelope system, with the exception of the Trial Statistician and the Clinical Project Manager, will be unblinded to treatment allocation via email and with the treatment allocated accessible through a secure portal, prior to the procedure being performed.

Given the study design, the treating neurosurgeon and associated research team cannot be blinded to treatment allocation. The increased operating time will also result in the Neonatal Intensive Care Unit (NICU) team being aware of the treatment arm. Previous Patient Advisory Group (PAG) work has identified that parents would like to be informed of the allocation and, failing to do so may result in many parents not taking part.

However, the primary outcome measure and other components of the Bayley IV developmental outcomes at 2 years' corrected age will be carried out by assessors blind to the treatment allocation.

8.2.5 Allocation Implementation

Following confirmation of participant eligibility, eligible participants will be randomised at the 'Surgery (t=0)' visit by a clinical investigator or delegated member of the research team using the Sealed Envelope web-based service.

The responsibility for enrolling and performing the allocated surgical intervention (as per the procedures outlined in Section 4) for the participant lies with the PI at each recruiting participating site, however this can also be undertaken by other delegated clinicians who have been delegated the task and which has been recorded on the ENLIVEN-UK Delegation Log. Secure login usernames and passwords for Sealed Envelope will be provided to delegated staff prior to site activation and/or as required. A complete list of users can be obtained from UCL CCTU.

The users will be required to log in and answer eligibility questions before entering minimisation data and being permitted to randomise a participant. The randomisation result will be shown directly online, with an email confirmation to the user.

8.3 Statistical Considerations

8.3.1 Statistical Analysis Plan

This section should be considered as version 0.1 of the statistical analysis plan (SAP). Further detail will be provided in a standalone SAP document, written by the trial statistician and approved by the TMG and Data Monitoring Committee (DMC) prior to any substantial analysis of the data.

The SAP will be pre-specified and will be stored within the electronic Statistics Master File (SMF) in an access-protected network drive. It will contain the following sections:

- I. Introduction
- II. Study Methods
- III. Statistical Principles
- IV. Trial Population
- V. Analysis of Primary and Secondary Outcomes (including statistical models and method of dealing with missingness)

8.3.2 Summary of baseline data and flow of participants

A CONSORT diagram will be produced to report the flow of participants in the study.

Summaries of baseline characteristics, by trial arm, will be presented using frequency and percentage for categorical variables, and for continuous variables by mean and standard deviation (or median and inter-quartile range for non-normally distributed data).

The results of the analyses will be reported following the principle of the ICH E3 guidelines on the Structure and Content of Clinical Study Reports (30). The pilot/feasibility stage will take guidance from the dedicated CONSORT extension for trials of that type (31).

8.3.3 Interim Analyses

No formal interim analyses are currently planned beyond regularly scheduled Independent Data Monitoring Committee (IDMC) meetings and an internal pilot study focussed on recruitment and adherence. The IDMC has responsibility for safeguarding the interests of trial participants and advises the Trial Steering Committee (TSC). This is done by providing the IDMC with reports on safety and efficacy to assess benefit/risk ratio on trial conduct to ensure that the study can achieve its goals. The IDMC and its delegates will have unrestricted access to unblinded data and will direct the unblinded statistician to facilitate reports as they require.

8.3.4 Internal Pilot

An internal pilot study will be conducted over the first 12 months of recruitment, beginning when the first centre opens. This pilot study will have specific aims of assessing recruitment feasibility, barriers to recruitment and protocol adherence with clear 'traffic light' progression criteria (Table 7). The progress of the trial will be reviewed by the TSC and Funder against the traffic light progression criteria. However, the Funder will be central to decision-making at the end of the pilot phase under all scenarios described below:

- Red: No progression to substantive phase
- Amber: A 'Recovery Plan' will be drafted in consultation with the TSC and the IDMC, ahead of consultation with the Funder over the terms of progression (or not) to the main phase of the study
- Green: Only a 'green' outcome would automatically qualify for automatic 'progression without change'.

An IDMC meeting will also be scheduled prior to progression past the pilot to ensure there are no safety concerns.

Table 7. Red/Amber/Green progression criteria for 12-month internal pilot study

	Red	Amber	Green
	No progression to substantive phase	A 'Recovery Plan' will be drafted over	Automatic progression to
		the terms of progression (or not) to the main phase of the study	substantive phase
Total sites opened	<5	5 to 7	8+

Patients screened per	<1	1 to <2	2+
site per 6 months open			
Patients recruited per	<0.3	0.3 to <1	1+
site per 6 months open			
Total patients recruited	10	11 to 19	20+
Adherence to	<70%	70 to 90%	>90%
randomised arm			

In addition, specific barriers to recruitment will be assessed:

Screening logs will be scrutinised to assess whether eligible patients have been
missed or not approached by study teams and structured questionnaires will be
conducted with the PI and Associate PI at each site to identify any reasons or
barriers. Parents who decline participation will be asked to volunteer the reason for
not taking part.

Any modifiable barriers (e.g., nature of approach, information sheets) will be addressed prior to commencement of the substantive phase of the trial.

8.3.5 Statistical Methods - Primary Outcome

As described in the sample size section the primary outcome measure will be the cognitive quotient (CQ) scale rescaled to range from 0—100. The outcome measure will be assessed at the infant's 2 years corrected age timepoint only and we anticipate that the shapes of the two response distributions will differ. As this continuous outcome scale is not normally distributed and the sample sizes are of moderate size the non-parametric Mann Whitney U test will be used to compare the two independent arms. This will test the alternative hypothesis that responses in the two arms are not equal. This test will be performed two-sided and at a 5% alpha level. The test statistic for the Mann Whitney U Test is denoted by U and is derived using the sums of the ranks within arms of responses in both groups. U₁ (NEL with Temporising Device) and U₂ (Temporising Device Alone) will then be compared. An exact p-value will be calculated rather than a normal approximation. The effect measure will be the median difference in rescaled CQ score along with a 95% Confidence Interval. Sensitivity analyses will be performed adjusting for the minimisation factors to assess the robustness of the primary analysis, and separately the bootstrap means will also be calculated and compared between randomised groups.

8.3.6 Analysis Population and Missing Data

It is only possible to include those randomised infants with 2 year response data in the primary analysis. This is effectively what is termed a 'complete case analysis'. Naturally, it is key that missing data, for the Bayley-IV questionnaire in particular, at the two year timepoint is kept to the absolute minimum due to its potential to undermine the primary conclusions to be drawn from the trial. Multiple Imputation of missing values is possible, though consideration will need to be taken as to the volume and mechanism behind the missing data and its consequent effect on the interpretation of the outcome measure. This will be expanded upon further using the estimand framework in further iterations of the SAP. All infants randomised to one of the two arms will be included in other analyses where possible, irrespective of the successful completion of the procedure as intended – following the Intention to Treatment principle and analysis set. Any infants withdrawn after consenting, but prior to randomisation and surgery, will be summarised clearly and openly separately. Exploratory analyses may be produced using only those that adhered to the protocol as intended (Per Protocol) should the analysis aid interpretation.

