1.1.1 Explanation for choice of comparators

Several interventions for PHVD have been tested in randomised trials and non-randomised studies at various stages of the treatment pathway. Although in the past, treatment was only started once the ventricles were large enough to raise intracranial pressure and cause symptoms with overt neurological deterioration, recent studies have suggested that earlier treatment, based on standardised ultrasound measurements of ventricular size, is beneficial (14,15). Across the UK, the majority of paediatric neurosurgical units have taken a ventricular size of 4mm above the 97th centile as the treatment threshold.

The use of acetazolamide and furosemide to reduce CSF production resulted in increased death, disability or impairment and probably increased requirement for a VP shunt (16). Repeated taps, lumbar punctures and intraventricular streptokinase to remove clot from CSF pathways also did not improve outcome (17,18).

The DRIFT (Drainage, Irrigation, Fibrinolysis Trial) study was the first trial to demonstrate a significant reduction in the proportion of children with severe cognitive disability or death at follow-up at two and ten years (13,19,20). The improved cognition at ten years was equivalent

to a two-year developmental improvement. This suggested that effective washout of blood from the CSF may limit the extent of brain injury. DRIFT involves the insertion of two catheters into the ventricles of a premature infants: irrigating fluid flows in through one and out through the other. The irrigation is continued for about five days, during which very close and specialist monitoring of fluid flow and intracranial pressure is required. DRIFT also requires the use of fibrinolytic agents, and a proportion of babies had secondary bleeds in the ventricles following treatment. The DRIFT technique requires specialist and dedicated expertise over a long period of time, and is difficult to implement, teach and disseminate. Development of techniques that enable easier lavage of intraventricular blood, ideally contained within a single brief surgical procedure, is required.

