- 4. Any change in the participant's condition that in the clinician's opinion justifies the discontinuation of trial follow-up after the surgery has been completed.

Intra-operative discontinuation of the NEL (due to complications or technical difficulties as listed in the operative CRF) does not mandate removal of the participant from the trial. Any subsequent treatment following intra-operative discontinuation of the NEL will be at the treating clinician's discretion.

As participation in the trial is entirely voluntary, the parent/legal guardian(s) may choose to discontinue participation of their infant for trial follow-up and data collection at any time without penalty or loss of benefits to which they would otherwise be entitled. Although not obliged to give a reason for discontinuing participation, a reasonable effort should be made to establish this reason, whilst remaining fully respectful of their rights.

It should be clear to the parent/legal guardian(s) and recorded in the patient notes what aspect(s) of the trial the participant is discontinuing their participation. These could include:

- Early cessation from sample collections
- Early cessation from questionnaires
- Early cessation from further trial follow-up
- Early cessation electronic health record use.

Patients should remain in the trial for the purpose of follow-up and data analysis (unless the parent/legal guardian(s) withdraws their consent from all stages of the trial). If a patient ceases follow-up early, refer to Section 5.5.

Data on patients who stop follow-up early will be kept and included in analyses where possible. Infants that are withdrawn by their parent/guardian(s) after having had their baseline data collected, but prior to randomisation, will be recorded as withdrawals. As they will not have been randomised, they will not count towards the target sample size though their baseline data will still be summarised at the reporting stage. Infants who are withdrawn after they have

undergone surgery (either Arm A NEL with Temporising Device or Arm B Temporising Device alone), will not be able to withdraw from the surgical part of the trial, only from trial follow-up visits. Participant's parent/guardian(s) will be fully advised of this at the time of consent for the trial and the time of consent for the surgical procedure.

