9.2 Within-trial analysis

An economic evaluation will be conducted over the trial period with a primary analysis from the NHS and personal social services (PSS) perspective and a secondary analysis from the societal perspective that will include the impact on quality of life and productivity of parents/carers contributing to the infant's care. Discount rate of 3.5% currently recommended for health technology appraisal in the UK (33) will be applied to costs and health effects accruing beyond the first year. The overall economic evaluation will comprise:

- 1. Cost-Effectiveness Analysis: mean incremental costs and incremental effectiveness of NEL + temporising device compared with temporising device alone. Incremental costs will be measured from the NHS and PSS perspective. Incremental effectiveness will be estimated as the difference in cognitive disability at 2 years' corrected age. Data on delivery of the NEL intervention (e.g., staff time, consumables) will be collected to calculate the cost of the intervention using micro-costing methods (34). Additional healthcare resource use such as days in hospital, number of planned and emergency admissions will be collected at 3-6, 12, 18 months and 2 years' corrected age through purpose designed parent-completed questionnaires (telephone assessment). Unit costs will be obtained from most recent published sources (35,36). Incremental cost-effectiveness ratios will be reported, and uncertainty explored using cost-effectiveness acceptability curves (37,38)
- 2. Health-Related Quality of Life (HRQoL): measuring the overall impact of a health condition requires preference-based methods. Efforts to evaluate HRQoL and calculate quality-adjusted life years (QALYs) for infants less than 12 months of age are restricted by the lack of preference-based HRQoL instruments for this group (39,40). Because of methodological concerns surrounding the use of preference-based

measurement in early childhood, the QALY metric will not be used. However, we will assess the HRQoL (at 1 year and 2 years' corrected age) using the TAPQOL (TNO-AZL Preschool Children's Quality of Life) a reliable and valid instrument for measuring parent's perceptions HRQoL for children aged between 1 and 5 years (41).

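### The protocol wrongly calls a complete-case primary analysis the only option: infants who die leave the CQ comparison, and no listed sensitivity analysis brings them back

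*Protocol*

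**What the plan says.** Section 8.3.6 restricts the primary analysis: "It is only possible to include those randomised infants with 2 year response data in the primary analysis". It adds: "This is effectively what is termed a 'complete case analysis". The intention-to-treat set of all randomised infants is kept for the other analyses, where possible.

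On missing scores, the same section says: "Multiple Imputation of missing values is possible, though consideration will need to be taken as to the volume and mechanism behind the missing data". It then defers: "This will be expanded upon further using the estimand framework in further iterations of the SAP".

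Other relevant places:

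- Section 5.1.1 defines CQ as the Bayley IV age-equivalent cognitive score over corrected age, times 100. It sets no value for a child who has died or could not be tested.
- Section 8.3.5 specifies a two-sided 5% Mann-Whitney U test. The sensitivity analyses listed are adjustment for the minimisation factors and a comparison of bootstrap means.
- Sections 5.1.2 and 8.3.7 make mortality to 2 years a secondary outcome with a log-rank test. The motor and language quotients follow the primary method.
- Section 6.3 (withdrawal of medical care) expects a small number of deaths after such decisions, some after randomisation.
- Section 8.1 inflates 90 to 100 infants: "To account for a 10% loss to follow-up and other methodological challenges during the study". Deaths are not named.
- Section 1.1.1 describes the DRIFT result on which the trial builds as a "significant reduction in the proportion of children with severe cognitive disability or death at follow-up at two and ten years".

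**The concern.** A Mann-Whitney test uses ranks only. Death can be placed below every observed CQ without inventing a score, so the stated reason for restricting the population is wrong. The DRIFT result, as the protocol cites it, counted death together with severe disability.

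Restricting to infants with a score conditions on something that happens after randomisation. If one arm loses more of its poorest-prognosis infants, its survivors look better for that reason alone. Excess deaths on lavage would then appear as cognitive benefit, and excess deaths on control would hide a real benefit. Neither listed sensitivity analysis would show this, because both use the same survivors.

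The discontinuation text between sections 4.5 and 4.7 adds a related route to missing scores. One listed reason for ending follow-up is: "Any change in the participant's condition that in the clinician's opinion justifies the discontinuation of trial follow-up after the surgery has been completed". The same part, and section 5.5, ask that infants stay in follow-up and that every appropriate effort be made to complete the primary assessment.

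**Working it through.** **Inputs from section 8.1.** Control CQ is 100 × Beta(1,1), uniform on 0 to 100. Lavage CQ is 100 × Beta(10, 4.25). The test is a two-sided 5% Wilcoxon test, with 45 evaluable per arm and 50 recruited per arm.

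**Assumed.** All death rates and their relation to CQ, because the documents give none.

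**The plan's own figure.** The modelled medians are 50 and 71.1. Simulated power at 45 per arm is 91.4% (normal approximation) or 90.8% (exact), against the stated 90%; 90 / 0.9 = 100. The sample size reproduces. If exclusions go beyond the 10% allowance, power is 87.7% at 40 per arm and 83.6% at 35.

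**Size of the bias, by formula.** Remove the lowest fraction d of a uniform 0–100 arm. The survivors are uniform on (100d, 100), so their median is 50 + 50d.

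- No true effect, lavage loses its lowest 10%: 55 − 50 = +5 points. At 20%: 60 − 50 = +10 points.
- Design effect true, control loses its lowest 10%: 71.1 − 55 = 16.1 points instead of 21.1. At 20%: 71.1 − 60 = 11.1 points.

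**Simulation, 50 per arm, deaths strictly among the lowest CQ.** The rank analysis keeps all 100 infants with deaths lowest.

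| Truth | Deaths lavage / control | Complete case | Rank analysis with deaths lowest |
|---|---|---|---|
| No CQ effect | 10% / 0% | favours lavage in 14% | rejects in 4–5% |
| No CQ effect | 20% / 0% | favours lavage in 36–38% | rejects in 4–5% |
| No CQ effect | 0% / 10% | favours control in 14.5% | rejects in 4% |
| Design effect | 0% / 10% | power 80% | power 93–94% |
| Design effect | 0% / 20% | power 55% | power 94% |

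The nominal rate in one direction is 2.5%. Ranges are the spread between simulation runs. With no deaths, power at 50 per arm is about 94%.

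**Milder selection, no true effect, 5% background deaths in both arms.**

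- Excess lavage deaths of 10 or 20 percentage points, three-quarters of them from the lower half of CQ: false benefit in about 4% or 7 to 8% of trials.
- Excess of 3 to 5 points, strictly lowest CQ: about 5 to 8%.

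**Deaths equal across arms and unrelated to CQ.** Complete case keeps the 21-point difference and rejects a true null at about 5%. Only power is lost.

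**Power cost of making the death-inclusive ranking primary, design effect true, random deaths equal in both arms.**

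- 10% per arm: about 91% falls to about 82% (80 to 84%, depending on whether the number of deaths is random or fixed).
- 20% per arm: about 88% falls to 61 to 67%.

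**The case against.** The case for the plan is substantial.

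- **Deferral.** Section 8.3.1 calls this part version 0.1 of the SAP, and section 8.3.6 leaves the estimand to later versions. A strategy for death commonly sits there. That stands for the detail. It does not undo the population that the protocol already fixes, or the reason given for it.
- **Mortality is not ignored.** It has its own log-rank analysis, and every death goes promptly to the IDMC (section 6.5). With 5% background deaths, a simple two-proportion comparison would flag a 10- or 20-point excess in about 36% or 83% of trials. In the strict-selection scenarios the rank analysis avoids the false benefit but does not reveal the harm. So mortality by arm must be shown beside it. A separate mortality test still does not correct the CQ p-value.
- **The large figures need strict selection.** Section 1.4 puts the additional lavage risks below 5% and does not expect risks significantly above control. With softer selection the error is small. This stands.
- **A composite is another estimand.** True. Making it primary is a choice with a power cost, not a correction.

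Three stronger readings are tempting but unsupported. A reader might infer that the plan discards children too impaired to test. It never says so: the scale reaches 0, so a very impaired child who can be tested is kept, and the gap is silence about a child with no score. A reader might carry the flaw into the economic analysis, where "Incremental effectiveness will be estimated as the difference in cognitive disability at 2 years' corrected age" is the effectiveness measure. Section 9.2 does not define that as complete-case CQ, and detail is left to the health economic analysis plan. A reader might also infer that the plan imputes scores for dead infants; section 8.3.6 proposes no such thing.

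**Conclusion.** The point holds in limited form. The claim that no other primary population is possible is untrue for the specified test. The protocol fixes a survivor comparison without saying how death is to be interpreted, and lists no analysis that would reveal bias from it.

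The bias can run either way. Its size depends wholly on assumed death rates and selection, from none to a false benefit in more than a third of trials under the strictest 20% assumption. The documents do not show that such a pattern is likely, nor that the death-inclusive ranking must become the primary analysis. Because the arm is known to the treating team and deaths are expected, the rule should be set before any unblinded data are seen.

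**What to change.** 1. In section 8.3.6, delete the statement that no other population is possible, and state the primary estimand's strategy for death.
2. Pre-specify, as a key supporting analysis, a rank analysis of all randomised infants with known outcome: death lowest, then alive but untestable because of severe impairment, then observed CQ. Report it beside the primary result with mortality by arm, and interpret any claim of benefit in light of both.
3. Record the reason for every missing Bayley assessment.
4. Limit any imputation to infants who are alive but lost for other reasons.
5. Reconcile the fourth listed reason for stopping follow-up with the statements in the same part and in section 5.5 that infants should remain in follow-up.

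The cost is wording, one more analysis and one CRF field. Whether the composite should become primary is the sponsor's trade-off: it changes the question to survival and cognition together, and the power loss shown above would reopen the sample size.
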